# 3.4.7 SPONSOR Responsibility for Reporting Adverse Experiences

All adverse experiences will be reported to regulatory agencies, IRB/IECs, and investigators in accordance with all applicable global laws and regulations.

### 3.5 STATISTICAL ANALYSIS PLAN (SAP)

# 3.5.1 Responsibility for Analysis

This section details the statistical analysis strategy and procedures for this study. If, after the study has begun, but prior to any unblinding, changes are made to the primary objective, or the statistical methods related to this objective, then the protocol will be amended (consistent with ICH Guideline E-9). Changes to secondary or and/or statistical analyses made after the protocol has been finalized, along with an explanation as to when and why they occurred, will be listed in the Clinical Study Report (CSR) for the study.

# 3.5.2 Responsibility for Analyses/In-House Blinding

The statistical analysis of the data obtained from this study will be the responsibility of the Clinical Biostatistics department of the SPONSOR (or its designee).

Because this is a double-blind with in-house blind study, the investigator, study participant, and SPONSOR personnel (or their designees) will remain blinded to the IV antifungal study therapy regimen. In order to maintain this blind, preparation and administration of the IV study therapy must be performed by someone other than the person(s) who will evaluate the patient for efficacy response and presence of adverse experiences. As these 2 products differ in color, opaque masking will be used over the infusion materials (e.g., infusion syringe and tubing) to ensure adequate blinding of the treatment group.

Unblinding of the data will not take place until medical/scientific review has been performed, protocol violators have been identified, and the data have been declared final and complete.

#### 3.5.3 Hypotheses/Estimation

Objectives and hypotheses of the study are stated in Section 2.1 (Objectives and Hypotheses).

# 3.5.4 Analysis Endpoints

Efficacy and safety endpoints that will be evaluated for between-treatment differences are listed below.

# 3.5.4.1 Efficacy/Pharmacokinetic Endpoints

#### 3.5.4.1.1 Pharmacokinetic Endpoints

Pharmacokinetic (PK) profile ( $C_{max}$  [peak],  $C_{24 hr}$  [trough]) of the administered dose of caspofungin will be determined for neonates and infants less than three months of age on

**Protocol/Amendment No.:** 064-02

or around Days 4 and 7 of study therapy. Pharmacokinetic profiling will be the responsibility of the Drug Metabolism department of the SPONSOR (or its designee).

# 3.5.4.1.2 Efficacy Endpoints

An initial description of efficacy measurements is provided in Section 3.3.1.

The primary efficacy endpoint of interest will be fungal-free survival at two weeks posttherapy. Fungal-free survival is defined as those patients who survived at the time point of interest and had documented microbiological eradication of *Candida* sp. from follow-up cultures collected after the initiation of study therapy. Microbiological eradication denotes negative follow-up cultures for *Candida* sp. from the site of infection at the time of evaluation. If a culture is not obtained on the day of assessment, the last culture after study entry may be used to assist in the assessment of microbiological eradication. If the last culture is negative for *Candida* sp., then microbiological eradication would be considered achieved. Fungal-free survival also assumes no additional antifungal therapy is required for the treatment of the underlying *Candida* infection once study therapy has ended; however, once study therapy has ended, prophylaxis with an antifungal agent (e.g., fluconazole) may be administered, if this is deemed appropriate by the investigator.

The secondary efficacy endpoint will be fungal-free survival at the end of study therapy.

#### 3.5.4.2 Safety Endpoints

There are no safety parameters that rise to the level of formal statistical testing for this study (i.e., no Tier 1 events).

To address the secondary safety objective, the following safety endpoints will be evaluated: (1) the development of adverse experience(s) during the study therapy period or during the 2-week posttherapy follow-up period; (2) the development of drug-related adverse experience(s) during the study therapy period or during the 2-week posttherapy follow-up period; (3) the development of serious adverse experience(s) during study therapy period or during the 2-week posttherapy follow-up period; (4) the development of drug-related, serious adverse experience(s) during study therapy period or during the 2-week posttherapy follow-up period; (5) the development of adverse experiences that

**Protocol/Amendment No.:** 064-02

necessitate discontinuation of study therapy; and (6) the development of drug-related adverse experiences that necessitate discontinuation of study therapy.

# 3.5.5 Analysis Populations

# 3.5.5.1 Efficacy Analysis Populations

All efficacy evaluations will use the Full Analysis Set (FAS) patient population, which includes those patients who receive at least 1 full dose of study therapy and have a documented (culture-confirmed) diagnosis of invasive candidiasis. All patients, irrespective of body weight at study entry, will be grouped together for the primary evaluation. Subgroup evaluation based on the 3 body weight categories at study entry (<1000 grams, 1000-1500 grams, >1500 grams) will also be displayed.

A supportive analysis using the Per-Protocol population will be performed for the primary and secondary efficacy endpoints. The Per-Protocol population excludes patients due to important deviations from the protocol that may substantially affect the results of the primary and secondary efficacy endpoints. Inclusion within the per-protocol population mandates meeting all of the following:

- The patient must have a documented (culture-confirmed) diagnosis of invasive candidiasis.
- The patient must not receive >1 day of concomitant systemic antifungal therapy while on study therapy, if the total duration of study therapy is 3 weeks or less. For durations of study therapy exceeding 3 weeks, the patient must not receive concomitant systemic antifungal therapy while on study therapy, that amounts to more than 5% of the total duration of study therapy.
- The patient must have a 2-week posttherapy efficacy evaluation, including an appropriate microbiological assessment completed either at this visit or confirmed prior to that visit.
- The patient must receive at least 5 full days of study therapy.

The patient must not commit any protocol violations that interfere with the assessment of efficacy.

The final determination on protocol violations, and thereby the composition of the Per-Protocol population, will be made prior to the final unblinding of the database and will be documented in a separate memo. A patient who violates the protocol at randomization (e.g., certain inclusion or exclusion criteria, such as the use of prohibited prior treatment) will be excluded from the Per Protocol population. For patients who violate the protocol during the study (e.g., taking prohibited concomitant medication), data obtained subsequent to the violation will be excluded from analysis.

Patients who receive incorrect study medication for their entire treatment period will be counted in the treatment group for the treatment actually received. Otherwise, patients will be included in the treatment group to which they are randomized for the analysis of

**Protocol/Amendment No.:** 064-02

efficacy data using both the FAS and Per-Protocol populations. In the event 3 or more patients receive the incorrect study medication for their entire treatment period, a sensitivity analysis will be performed with such patients included in the treatment group to which they were initially randomized for the analysis of efficacy data using both the FAS and Per-Protocol populations. Details on the approach to handling missing data are provided in Section 3.5.6 (Statistical Methods).

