### Study Drug Preparation

Caspofungin will be administered at 2 mg/kg once daily (with no loading dose). Dosing with caspofungin will be based on the patient's actual weight at the time of study entry.

Caspofungin will be reconstituted/prepared by an unblinded study pharmacist. Appropriate quantities of caspofungin will be diluted with normal (0.9%) saline to achieve a final concentration not to exceed 0.5 mg/mL. For example, for a 1-kg neonate, the daily caspofungin dose is 2 mg, and should be diluted in at least 4 mL. **NOTE:** Dilution of caspofungin in dextrose-containing solutions is contraindicated. The final total volume of infusate is at the discretion of the unblinded pharmacist and should be based on the patient's ability to tolerate the fluid load. However, the final caspofungin concentration should not exceed 0.5 mg/mL. Full guidelines for the preparation of caspofungin study therapy for infusion are provided in the Pharmacy Binder.

Amphotericin B deoxycholate will be administered at 1 mg/kg (per body weight) once daily. Amphotericin B deoxycholate will be reconstituted/prepared by an unblinded study pharmacist. Dosing with amphotericin B deoxycholate will be based on the patient's actual weight at the time of study entry. The amphotericin preparation will also be administered as a single daily infusion. Full guidelines for the preparation of amphotericin B deoxycholate study therapy for infusion are provided in the Pharmacy Binder

In order to verify the patient is receiving the correct dose of either caspofungin or amphotericin B deoxycholate, weight should be measured at least once weekly while the patient is on study therapy, and the dose of caspofungin or amphotericin B deoxycholate should be adjusted accordingly.

All study therapy (caspofungin or amphotericin B deoxycholate) will be administered intravenously as a single daily dose. Each infusion should be administered over approximately 2 hours. The IV line should be flushed thoroughly after each study therapy infusion. Infusion of study therapy may be given through either a pediatric syringe pump or ambulatory pump if this will help ensure that the patient receives the complete dose.

As these 2 products differ in color, opaque masking will be used over the infusion materials (e.g., infusion syringe and tubing) to ensure adequate blinding of the treatment

**Protocol/Amendment No.:** 064-02

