#### 2.8 STATISTICAL ANALYSIS PLAN SUMMARY

Key elements of the statistical analysis plan are summarized below; the comprehensive plan is provided in Section 3.5 of the protocol details.

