#### 2.8.1 Efficacy Analyses

The primary and secondary endpoints, primary analysis population, and statistical methods that will be employed for the efficacy analyses are presented in Table 2-2.

**Protocol/Amendment No.:** 064-02

The primary hypothesis will be evaluated by comparing the caspofungin treatment group to the amphotericin B deoxycholate treatment group with respect to the proportion of patients with fungal-free survival at the 2-week posttherapy follow-up visit.

All efficacy evaluations will use a full analysis set (FAS) patient population, which includes those patients who receive at least one dose of study therapy and have a documented (culture-confirmed) diagnosis of invasive candidiasis (see Section 2.2, Inclusion Criteria). All patients, irrespective of body weight at study entry, will be grouped together for the primary evaluation. Subgroup evaluation based on the 3 body weight categories at study entry (<1000 grams, 1000-1500 grams, >1500 grams) will also be displayed. Of note, a per-protocol population will also be evaluated for the primary and secondary efficacy endpoints (see Section 3.5.5.1, Efficacy Analysis Populations).

The treatment comparisons for the primary and secondary efficacy analyses will be made using the difference in response rates between the 2 treatment groups and its 95% confidence interval. The confidence interval for the difference in response rates will be calculated using a methodology proposed by Miettinen and Nurminen [17].

**Protocol/Amendment No.:** 064-02

Table 2-2
Analysis Strategy for Key Efficacy Variables

	Primary vs.							
Endpoint/Variable	Supportive		Analysis	Missing Data				
(Description, Time Point)	Approach a	Statistical Method	Population	Approach				
Primary								
Proportion of patients with fungal-free survival through the 2-week posttherapy period	P	Miettinen and Nurminen method	FAS	A patient with missing data will be considered a failure.				
Proportion of patients with fungal-free survival through the 2-week posttherapy period	S	Miettinen and Nurminen method	PP	Observed data				
Secondary								
Proportion of patients reporting fungal-free survival at the end of study therapy	P	Miettinen and Nurminen method	FAS	A patient with missing data will be considered a failure.				
		Miettinen and		Observed data				

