#### Other Adverse Experiences

While receiving study therapy, patients who develop any adverse experience that is felt to possibly be related to the study drug, and for which interruption of therapy is clinically indicated, should have their study therapy stopped.

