# 3.5.5.2 Safety Analysis Population

The All Patients as Treated (APaT) population will be used for the analysis of safety data in this study. The APaT population consists of all randomized patients who received at least one dose of study treatment. Patients will be included in the treatment group corresponding to the study treatment they actually received for the analysis of safety data using the APaT population. For most patients, this will be the treatment group to which they are randomized. Patients who take incorrect study treatment for the entire treatment period will be included in the treatment group corresponding to the study treatment actually received.

At least one laboratory or vital sign measurement obtained subsequent to at least one dose of study treatment is required for inclusion in the analysis of each specific parameter. To assess change from baseline, a baseline measurement is also required.

Details on the approach to handling missing data for safety analyses are provided in Section 3.5.6 (Statistical Methods).

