# 3.5.6.1 Statistical Methods for Efficacy Analyses

The primary efficacy analysis will compare the caspofungin treatment group to the amphotericin B deoxycholate treatment group with respect to the proportion of patients with fungal-free survival at the 2-week posttherapy period. The minimum criterion for success is that the lower bound of 95% CI for the difference between the 2 treatment groups (caspofungin minus amphotericin B deoxycholate) in the primary efficacy endpoint is >0.

**Protocol/Amendment No.:** 064-02

The treatment comparisons for the primary and secondary efficacy analyses will be made using the difference in response rates between the 2 treatment groups and its 95% confidence interval. The confidence interval for the difference in response rates will be calculated using a methodology proposed by Miettinen and Nurminen [17].

Patients who have missing data for a given endpoint at the timepoint of interest will be counted as a failure for that endpoint at that timepoint.

Also, the caspofungin efficacy results from this study will be compared descriptively to the efficacy results for patients with invasive candidiasis in a prior Phase II pediatric documented infection study (Protocol 043, children and adolescents aged 3 months to 17 years) and prior Phase III adult studies (Protocols 014 and 801).

Table 3-6 summarizes the key efficacy analyses.

**Protocol/Amendment No.:** 064-02

Table 3-6
Analysis Strategy for Key Efficacy Variables

En du sint/Mariable	Primary vs.		A malania	Missing Data		
Endpoint/Variable (Description, Time Point)	Supportive Approach †	Statistical Method	Analysis Population	Missing Data Approach		
Primary						
Proportion of patients with fungal-free survival through the 2-week posttherapy period	P	Miettinen and Nurminen method	FAS	A patient with missing data will be considered a failure.		
Proportion of patients with fungal-free survival through the 2-week posttherapy period	S	Miettinen and Nurminen method	PP	Observed data		
Secondary						
Proportion of patients reporting fungal-free survival at the end of study therapy	P	Miettinen and Nurminen method	FAS	A patient with missing data will be considered a failure.		
Proportion of patients reporting fungal-free survival at the end of study therapy	S	Miettinen and Nurminen method	PP	Observed data		
P=Primary approach; S=Secondary approach.						

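### The primary-analysis FAS has two definitions, and the stricter one, in Section 3.5.5.1, drops a treated infant who never completes an infusion

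*Combined protocol and SAP*

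**What the plan says.** Section 3.5.5.1 (Efficacy Analysis Populations) says that the FAS "includes those patients who receive at least 1 full dose of study therapy" and also have a culture-confirmed diagnosis. Section 2.8.1 (Efficacy Analyses) says that the same FAS "includes those patients who receive at least one dose of study therapy", with the same diagnostic condition. Both sections apply this set to all efficacy evaluations, so both govern the primary comparison.

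Section 2.8 presents itself as a summary and says that "the comprehensive plan is provided in Section 3.5 of the protocol details". The safety population in Section 3.5.5.2 is "all randomized patients who received at least one dose of study treatment", again without *full*. I found no definition of a full dose.

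Two other passages matter. On administration, Section 2.4.2 says: "Each infusion should be administered over approximately 2 hours". On tolerability, Section 3.4.2 (Other Adverse Experiences) says that infants with a possibly drug-related event, where interruption is clinically indicated, "should have their study therapy stopped".

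**The concern.** A two-hour infusion can be left incomplete. An infant might be stopped for an adverse experience, or die, during the first infusion and not be dosed again. That infant has been randomised and exposed and counts for safety. The infant is in the FAS under Section 2.8.1 and out of it under Section 3.5.5.1.

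Completing a dose happens after randomisation and can depend on the drug assigned. Selecting the primary population on it weakens the randomised comparison. The infants concerned are also likely to be failures on fungal-free survival, through death or a need for other antifungal treatment. With about 30 infants in the comparator arm, each one counts for something.

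The plan's other safeguards do not reach this case:

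- **Missing data.** Section 3.5.6.1 says "Patients who have missing data for a given endpoint at the timepoint of interest will be" counted as failures. That rule works inside the analysis set and cannot restore someone excluded from it.
- **Sensitivity analysis.** The one attached to the analysis populations in Section 3.5.5.1 concerns infants given the wrong medication throughout.
- **Blinded memo.** The memo to be written before unblinding settles the Per-Protocol population; Section 3.5.5.1 names no such step for the FAS.

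**Working it through.** **Inputs from the documents.** Randomisation is 2:1, about 60:30, and the design rates are 80% vs 50% (Section 3.5.8.1, Table 3-8). Success means that the lower Miettinen-Nurminen 95% bound for caspofungin minus amphotericin B exceeds 0 (Section 3.5.6.1).

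**Assumptions.** The documents give no rate of infants who never complete a dose. I take 0 to 2 per arm, with 3 as a stress case, and assume that each is a failure.

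**Step 1: the plan's own figures.** With k = 2, the pooled two-proportion formula for the control arm is

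n = [1.96·√((1+1/k)·p̄(1−p̄)) + 0.842·√(p₂(1−p₂) + p₁(1−p₁)/k)]² / (p₁−p₂)²

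Here p̄ = (0.5 + 2×0.8)/3 = 0.70, so n = [1.96·√0.315 + 0.842·√0.33]² / 0.09 ≈ 27.9. Rounded up this is 28, giving 56:28 = 84, as in Table 3-8. The FAS wording does not affect this arithmetic.

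The interval code was checked against Table 3-9. For 3/60 vs 3/30 it gives (-21.3, 5.9) against the printed (-21.2, 5.9). For 6/60 vs 9/30 it gives (-39.2, -3.4) against (-39.1, -3.5). Agreement is within 0.1 point.

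**Step 2: who is affected.** The text asks for at least one full dose, not a full first dose. An infant whose first infusion is cut short but who later completes one stays in the FAS. Only an infant who never completes any infusion is lost.

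**Step 3: effect on the decision.** The lower bound exceeds 0 exactly when the score statistic at zero difference exceeds 1.96:

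Z = (p₁−p₂) / √[p̄(1−p̄)(1/n₁+1/n₂)·N/(N−1)], where p̄ is now the pooled observed proportion.

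- 43/60 vs 15/30: p̄ = 58/90 = 0.644, Z = 0.2167/0.1076 = 2.01, success.
- 43/60 vs 15/29: p̄ = 58/89 = 0.652, Z = 0.1994/0.1084 = 1.84, not success.

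The full intervals, in percentage points, are:

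| Result | Excluded | Difference (95% CI) | Success |
|---|---|---|---|
| 43/60 vs 15/30 | none | 21.7 (0.6, 41.9) | yes |
| 43/60 vs 15/29 | 1 amphotericin B failure | 19.9 (-1.2, 40.6) | no |
| 43/60 vs 15/28 | 2 amphotericin B failures | 18.1 (-3.1, 39.1) | no |
| 44/60 vs 15/30 | none | 23.3 (2.3, 43.4) | yes |
| 44/60 vs 15/29 | 1 amphotericin B failure | 21.6 (0.5, 42.1) | yes |
| 42/60 vs 15/30 | none | 20.0 (-1.2, 40.4) | no |
| 42/58 vs 15/30 | 2 caspofungin failures | 22.4 (1.2, 42.7) | yes |
| 48/60 vs 15/30 | none | 30.0 (9.5, 49.5) | yes |
| 48/60 vs 15/27 | 3 amphotericin B failures | 24.4 (3.8, 45.2) | yes |

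Each lost amphotericin B failure lowers the bound by about 1.8 points near the boundary (0.6 to -1.2). Each lost caspofungin failure raises it by about 1.2 points (-1.2 to 1.2 over two).

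**Step 4: how often it would matter.** I enumerated all outcomes at 80% vs 50% with 60:30. If one amphotericin B failure were removed from every trial, the verdict would change in about 5.0% of trials.

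**The case against.** The strongest reply is that this is a wording slip with little practical reach. Much of that reply stands.

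- Section 2.8 gives a basis for precedence, and Section 3.5.2 holds unblinding until the data are final. The conflict can be settled blind.
- Few infants should be affected. Section 3.4.2 allows therapy to be withheld and restarted, infants not expected to survive five days are excluded, and Section 3.5.10 expects missed or incorrect dosing to be uncommon. Zero cases is plausible.
- A result resting on the threshold can be moved by any single outcome.
- Counting any part of a dose still conditions on treatment having started. The change is one of degree, although an infant who received no drug cannot have been excluded by the drug's effect.

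Stronger readings are tempting, but the documents do not support them:

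- **That any interrupted first infusion removes the infant.** The text does not say *first*.
- **That arm-dependent loss is already shown.** A reader might take it from Table 3-1, where 5/17 on amphotericin B and 0/15 on caspofungin discontinued for adverse events. Those counts carry no timing, and nothing places any of them before a completed dose. Table 3-3 reports no immediate local or systemic events in a series with 34 infants on amphotericin B.
- **That the rule favours the sponsor.** Losing amphotericin B failures raises the comparator rate and makes superiority harder to show.
- **That one exclusion generally reverses the result.** It does so at 43/60 vs 15/30 but not at 44/60 vs 15/30.

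Precedence does not answer the remaining point. It selects the stricter wording, which is the one that excludes treated infants.

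**Conclusion.** The point holds in limited form. The two sections give different definitions of the primary population. The version that appears to govern can exclude a randomised, exposed infant because of a post-randomisation event that may depend on the arm, and no rule I found in the plan brings that infant back.

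The expected effect is small. It rests on an assumed 0 to 2 infants per arm who never complete a dose, all taken to be failures. Under that assumption the decision can change in either direction when the observed difference is a little over 20 points, and it does not change at the design difference of 30 points. Arm dependence is a possibility created by the rule, not something the documents demonstrate. The sample size is unaffected.

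**What to change.** Before unblinding, delete *full* from the FAS definition in Section 3.5.5.1. State in both 3.5.5.1 and 2.8.1 that receipt of any part of a dose qualifies, together with the culture-confirmed diagnosis. This matches the present wording of 2.8.1 and the exposure criterion of the safety population in 3.5.5.2. Infants with no completed infusion are then scored by the stated endpoint and the missing-equals-failure rule. If *full dose* is kept anywhere, define it.

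The cost is one deleted word and one added sentence, made through the protocol amendment that Section 3.5.1 calls for when methods tied to the primary objective change. It needs no new data and alters neither dosing nor sample size. The downside is that a few minimally exposed infants stay in the FAS.

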#### 3.2.3.4 Randomization and Stratification

After written consent has been obtained, all screening procedures have been completed, and all inclusion/exclusion criteria have been met, the patient will be assigned an allocation number. Once an allocation number is assigned, it cannot be re-assigned to another patient.

In an effort to strive for adequate representation of patients from different weight groups (reflective of patient gestational age) in both treatment arms, randomization will be stratified into 3 weight categories (based on weight at study entry): <1000 grams, 1000 to 1500 grams, and >1500 grams. Patients will be stratified into each of the weight categories in a manner consistent with the 2:1 randomization of caspofungin to amphotericin B deoxycholate.

A single patient/subject cannot be assigned more than 1 allocation number.

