# 3.5.8.3 Subgroup Analysis

No formal subgroup evaluations will be performed and 95% CIs will not be displayed. Only counts and percents will be displayed. For the main efficacy endpoint, the results will be displayed by gender and race. Subgroup evaluation by weight stratification categories (<1000g, 1000-1500g, >1500g) and use of prestudy systemic (oral or IV) antifungal prophylaxis, will also be displayed. Other subgroup evaluations, based on site of *Candida* infection, underlying demographics, or region, may also be performed.

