# 6.2 RISK FACTORS OF INVASIVE CANDIDIASIS IN NEONATES AND INFANTS LESS THAN 3 MONTHS OF AGE

Risk factors	Comments			
Classic risk (also described in adults)				
Use of multiple or broad spectrum antibiotics and/or prolonged use of antibiotics	The length of antibiotic treatment is as important as the spectrum of antibiotics used.			
Central venous catheters or prolonged intravascular catheterization				
Parenteral hyperalimentation or intravenous fat emulsion				
Colonization with Candida and/or previous episode of mucocutaneous candidiasis				
Risk factors unique to this age group				
Prematurity/ very low birth weight	~90% of affected neonates are very low birth weight (<1500 gm)			
Endotracheal tube or existing tracheostomy	Many neonates have some type of respiratory insufficiency			
Congenital malformations, including GI malformations and congenital heart disease	Most frequently seen in infants >2,500 gm at birth with prolonged NICU hospitalization			
Gastrointestinal tract diseases	Necrotizing enterocolitis and anatomical abnormalities requiring surgery			

**Protocol/Amendment No.:** 064-02

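### Randomisation is stratified by entry weight but the primary and secondary analyses are not; if weight is clearly prognostic, this gives up about 0.5 to 4.5 points of power

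*Combined protocol and SAP*

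**What the plan says.** Section 3.2.3.4 sets the design: "randomization will be stratified into 3 weight categories (based on weight at study entry): <1000 grams, 1000 to 1500 grams, and >1500 grams". Sections 1.5 and 2.4.2 say the same, with 2:1 allocation kept within each category.

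Section 3.5.5.1, and Section 2.8.1 in the same terms, sets the analysis: "All patients, irrespective of body weight at study entry, will be grouped together for the primary evaluation". For primary and secondary endpoints alike, Section 3.5.6.1 states: "The confidence interval for the difference in response rates will be calculated using a methodology proposed by Miettinen and Nurminen". Tables 2-2 and 3-6 name that method with no strata and no weights. Success is a lower 95% bound above 0 for caspofungin minus amphotericin B.

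The weight categories come back only in Section 3.5.8.3, as a display: "No formal subgroup evaluations will be performed and 95% CIs will not be displayed". No stratified sensitivity analysis is planned, and no reason is given for leaving the factor out.

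The grouping sentence names only the primary evaluation. That the secondary endpoint is also unstratified is inferred from the method text and the two tables.

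**The concern.** Stratified allocation makes the two arms nearly alike in weight mix, so differences between weight groups add little to the true variance of the treatment contrast. The pooled variance is built from the overall response rates and still includes those differences. If weight predicts fungal-free survival, the pooled standard error is too large, the interval too wide and the test conservative.

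The trial turns on one confidence bound with about 28 to 30 controls. Table 3-8 requires 84 evaluable patients for 80% against 50%, and Section 3.5.8.1 expects about 84, so there is no planned margin. A stratified interval would recover precision already built into the design. It would also deal with whatever imbalance remains from incomplete blocks and from exclusions from the full analysis set.

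**Working it through.** **Inputs from the documents.** Control rate 50%, difference 30 points (so 80% on caspofungin), 2:1 allocation, two-sided 5%, 80% power, about 90 randomised and about 84 evaluable (Section 3.5.8.1); 84 (56:28) required (Table 3-8).

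**Inputs assumed.** The documents give no response rate and no patient share by entry-weight category, so the stratum rates, the stratum shares and the block size are all assumptions. The nearest figure is in Appendix 6.2, where about 90% of affected neonates are under 1500 g. That is birth weight, not entry weight, so it is indirect.

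**Step 1: reproduce the plan's figure.** Average rate = (0.5 + 2×0.8)/3 = 0.7. Controls needed = [1.960×√(1.5×0.7×0.3) + 0.8416×√(0.5×0.5 + 0.8×0.2/2)]² / 0.30² = (1.100 + 0.483)² / 0.09 = 27.9, so 28. That gives 28 + 56 = 84, as stated. Power at 56:28 is 80.2% by this formula and 80.8% by exact binomial calculation of the Miettinen-Nurminen criterion.

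**Step 2: direction, by hand.** Take equal strata, no treatment effect and 50% overall. The pooled variance uses 0.5×0.5 = 0.25, but the variance that remains under stratified allocation is the mean within-stratum value.

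- Rates 30/50/70%: (0.21 + 0.25 + 0.21)/3 = 0.2233. SE ratio √(0.2233/0.25) = 0.945; effective critical value 1.960/0.945 = 2.07; two-sided type I error about 3.8%.
- Rates 20/50/80%: (0.16 + 0.25 + 0.16)/3 = 0.19. SE ratio 0.872; effective critical value 2.25; two-sided type I error about 2.5%.

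With a constant 30-point effect and control rates 30/50/70%, the variance is 0.1333/56 + 0.2233/28 = 0.01036, against an assumed 0.16/56 + 0.25/28 = 0.01179. The SE ratio is 0.94. The same sum gives 0.97 at a 30-point control-rate spread and 0.98 at 20 points.

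**Step 3: simulation at N=84.** There were 200,000 trials per scenario (Monte Carlo SE about 0.09 points on power). Stratum sizes were multinomial, with 2:1 permuted blocks of 6 within stratum. Caspofungin rates came from a common odds ratio set to give 80% overall against 50% overall in controls. The pooled score test was compared with the stratified score test using weights n1n2/(n1+n2); each is equivalent to its lower bound exceeding 0. A stratum with an empty arm was merged.

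| Stratum shares | Assumed control rates, or odds ratio heaviest vs lightest | Power pooled → stratified | Change (points) | Two-sided type I error, pooled vs stratified |
|---|---|---|---|---|
| Equal | no weight effect | 80.8 → 80.5% | -0.3 | |
| Equal | 40/50/60% | 80.9 → 81.2% | +0.3 | |
| Equal | 30/50/70% | 81.9 → 83.7% | +1.8 | 4.0 vs 5.1% |
| Equal | 20/50/80% | 83.4 → 87.9% | +4.5 | 2.6 vs 4.9% |
| 45/40/15% | 30/60/85% | 82.0 → 84.7% | +2.7 | 3.4 vs 5.0% |
| 72/18/10% | OR 1 | 80.7 → 80.4% | -0.3 | |
| 72/18/10% | OR 2 | 80.9 → 80.7% | -0.2 | |
| 72/18/10% | OR 4 | 81.2 → 81.7% | +0.5 | |
| 72/18/10% | OR 9 | 81.6 → 82.8% | +1.2 | |

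The 72/18/10 mix was chosen to match the Appendix 6.2 figure. Blank cells were not tabulated. The simulated type I errors agree with the hand figures in Step 2.

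Mean 95% interval width at N=84, pooled vs stratified, was 40.8 vs 40.9 points with no weight effect, 40.8 vs 39.7 at 30/50/70%, and 40.9 vs 38.3 at 20/50/80%. The interval code matches three Table 3-9 entries within 0.1 points; for 12/60 vs 12/30 it gives (-40.1, -0.5) against the stated (-40.0, -0.6).

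At N=90 the changes are similar: 83.1 → 82.9% with no effect, 84.3 → 86.1% at 30/50/70%, 85.9 → 90.1% at 20/50/80%, and 84.3 → 87.0% for the 45/40/15 mix.

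**Step 4: second simulation.** Separate code, with 400,000 runs per scenario at 56:28, covered equal, 40/35/25 and 60/30/10 mixes and effects constant on either the risk-difference or the log-odds scale. By spread in control rate between the lightest and heaviest strata, the change in power from stratifying was:

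- no spread: -0.4 points
- 10 points: -0.3 to -0.1
- 20 points: 0.0 to +0.7
- 30 points: +0.5 to +2.0
- 40 points: +1.1 to +3.8
- 60 points: +2.9 to +4.7

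**The case against.** The case for leaving the plan alone is real. Pooling is stated openly, it is unbiased, and where it departs from nominal it errs on the safe side for a superiority claim. The sample size was worked out for the same unstratified comparison, so test and power basis agree. The stated purpose of stratifying is representation of the weight groups in both arms, not precision. Nothing in the documents shows that entry weight predicts fungal-free survival: Section 3.1.1 and Appendix 6.2 concern the risk of acquiring infection. The 4.5-point gain comes from one strong scenario, equal thirds with rates 20/50/80%. Under the mix closest to the documents' own figure, the change runs from -0.3 to +1.2 points.

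Most of this stands, and it limits the weight of the point. The size depends on assumptions, and no validity problem exists. The argument from chance imbalance is also modest, since stratified allocation already does most of that work.

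It does not remove the point. The sponsor thought weight important enough to stratify on, calling it a reflection of gestational age, yet plans no adjusted estimate and gives no reason. The trade is uneven: a loss of at most about 0.4 points if weight does not matter, against a gain of up to about 4.5 if it matters strongly.

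**Conclusion.** The concern holds. The analysis ignores the randomisation strata, and the effect is conservative when weight is prognostic. About 0.5 to 4.5 points of power are given up if weight is clearly prognostic, meaning a control-rate spread of roughly 30 to 60 points with fairly even strata, or an odds ratio of about 4 or more when most infants fall in the lightest category. With a spread of 10 points or less there is nothing to recover, and stratifying costs 0.1 to 0.4 points.

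These sizes rest on assumed stratum rates and shares and on the design rates of 80% and 50%. Pooled power stays at 80.7% or above in every row of the table, so the plan's 80% is not undermined. The point is worth acting on because it is cheap, not because the planned analysis is wrong.

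**What to change.** In Sections 2.8.1, 3.5.5.1 and 3.5.6.1 and in Tables 2-2 and 3-6, make the primary and secondary comparison the weight-stratified Miettinen-Nurminen difference, using the three randomisation categories and Cochran-Mantel-Haenszel weights n1n2/(n1+n2). State that a stratum with an empty arm is merged with its neighbour. This arose in about 1% of simulated trials at N=84 with a 10% stratum (about 8 patients, roughly 3 of them controls) and essentially never with equal strata. Keep the unstratified interval as a sensitivity analysis. Section 3.5.8.1 and Table 3-8 can stay as they are, with a sentence saying that the sizing is unstratified.

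If pooling is kept as primary, give the reason and add the stratified interval as the sensitivity analysis.

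The cost is some wording and one programming option, with no new data and no added patients. Because the method for the primary objective changes, Section 3.5.1 requires a protocol amendment before any unblinding. If weight proves not to be prognostic, the price is about 0.1 to 0.4 points of power and an interval up to about 1% wider.
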